4.5.1.2 Topotecan

Subjects randomized to Arm B will receive treatment with topotecan 1.5 mg/m² IV infusion or 2.3 mg/m² oral capsule (round dose to nearest 0.25 mg) on Days 1 through 5 every 3 weeks (21 days). Refer to the local product label for more details.

Dosing Window: Subjects may be dosed no less than 14 days from the last dose of the previous cycle and no more than 3 days from scheduled dose. If an infusion cannot be administered at a scheduled visit, it should be administered as soon as possible. Subsequent dosing visits will follow every 3 weeks after the delayed dose.

A dose given more than 3 days after the intended dose date will be considered a delay. A maximum delay of 6 weeks between doses is allowed. Longer delays may be allowed following discussion with the Medical Monitor, as described in [Section 4.5.3.1](#).

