4.5.1.3 Amrubicin

Subjects randomized to Arm B will receive treatment with amrubicin 40 mg/m² on Days 1 through 3 every 3 weeks (21 days). Refer to the local product label for more detail.

Dosing Window: Subjects may be dosed no less than 16 days from the last dose of the previous cycle and no more than 3 days from scheduled dose. If an infusion cannot be administered at a scheduled visit, it should be administered as soon as possible. Subsequent dosing visits will follow every 3 weeks after the delayed dose.

A dose given more than 3 days after the intended dose date will be considered a delay. A maximum delay of 6 weeks between doses is allowed. Longer delays may be allowed following discussion with the Medical Monitor, as described in [Section 4.5.3.1](#).

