| Procedure | Cycle 1 Day 1 (C1D1) | Cycle 1 Day 8 (C1D8) | Each Cycle (Every 2 Weeks) on Day 1 (± 3 Days) | Notes |
|---|----------------------|----------------------|--|---|
| Exploratory Biomarker Assessments | | | | |
| Biomarker samples (██████, Whole Blood, Tumor Biopsy) | X | X | See Note | See Table 5.6-1 of Biomarker Sampling Schedule |
| Outcomes Research Assessments | | | | |
| Patient Reported Outcomes (PRO) | X | | See Note | For on-study visits: Assessments (Lung Cancer Symptom Scale and EQ-5D) will be performed prior to treatment. Assessments will be performed at each cycle on Day 1 for the first 6 months on study, then every 6 weeks thereafter for the remainder of the treatment phase. |
| Health Resource Utilization | | | X | Except Cycle 1. Note that concomitant medication collection will be included. |
| Study Drug | | | | |
| Administer Study Drug | X | | X | IVRS should be called within 1 day prior to study drug administration to receive vial assignment. Note: Treatment should begin within 3 business days of randomization. Subjects may be dosed no less than 12 days between doses and no more than 3 days from the scheduled dose. IVRS should also be contacted at upon discontinuation of treatment. |

ALP = alkaline phosphatase, ALT = alanine aminotransferase, AST = aspartate aminotransferase, BP = blood pressure, BUN = blood urea nitrogen, Ca = calcium, Cl = chloride, CNS = central nervous system, CT = computed tomography, ECG = electrocardiogram, ECOG = Eastern Cooperative Oncology Group, HR = heart rate, IVRS = interactive voice response system, K = potassium, LDH = lactate dehydrogenase, LFT = liver function tests, Mg = magnesium, MRI = magnetic resonance imaging, Na = sodium, NCI CTCAE = National Cancer Institute Common Toxicity Criteria for Adverse Events, O2 = oxygen, P = phosphorus, SAE = serious adverse event, T.Bili = total bilirubin, TSH = thyroid stimulating hormone, T3 = triiodothyronine, T4 = thyroxine, WOCBP = women of childbearing potential

Table 5.1-3: On-Treatment Assessments for Subjects Randomized to Arm B, Chemotherapy (CA209331)

| Procedure | Cycle 1 Day 1 of a 21-day Cycle (Every 3 Weeks ± 3 Days) (C1D1) | Cycle 2 to x Day 1 of a 21-day Cycle (Every 3 Weeks ± 3 Days) C2D1 to CxD1 | Notes |
|-----------------------------------|---|--|--|
| Safety Assessments | | | |
| Targeted Physical Examination | X | X | Within 72 hours prior to dosing |

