| 

 Whole Blood Tumor Biopsy | X | See Note | See Table 5.6-2 of Biomarker Sampling Schedule |
| Outcomes Research Assessments | | | |
| Patient Reported Outcomes (PRO) | X | See Note | For on-study visits: Assessments (Lung Cancer Symptom Scale and EQ-5D) will be performed prior to treatment. Assessments will be performed at each cycle on Day 1 for the first 6 months on study, then every 6 weeks thereafter for the remainder of the treatment period. |
| Health Resource Utilization | | X | Except Cycle 1. Note that concomitant medication collection will be included. |

Table 5.1-3: On-Treatment Assessments for Subjects Randomized to Arm B, Chemotherapy (CA209331)

| Procedure | Cycle 1 Day 1 of a 21-day Cycle (Every 3 Weeks ± 3 Days) (C1D1) | Cycle 2 to x Day 1 of a 21-day Cycle (Every 3 Weeks ± 3 Days) C2D1 to CxD1 | Notes |
|-----------------------|---|--|--|
| Study Drug | | | |
| Administer Study Drug | X (See Note) | X (See Note) | Topotecan: 1.5 mg/m ² administered as 30-minute IV infusion or 2.3 mg/m ² oral capsule (round dose to nearest 0.25 mg) once daily on Days 1 to 5 of a 21-day cycle. Amrubicin (upon investigator’s choice, where locally approved for 2nd line SCLC treatment): 40 mg/m ² administered as 5-minute IV infusion once daily on Days 1 to 3 of a 21-day cycle. IVRS should be called within 1 day prior to study drug administration to receive vial assignment. Note: Treatment should begin within 3 business days of randomization. Subjects assigned to topotecan may be dosed no less than 14 days between doses and no more than 3 days from the scheduled dose. Subjects assigned to amrubicin may be dosed no less than 16 days between doses and no more than 3 days from the scheduled dose. |

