| blood, tumor biopsy) | | | progression is optional. See Table 5.6-1 or Table 5.6-2 of Biomarker Sampling Schedule. |
| Outcomes Research Assessments | | | |
| Patient Reported Outcomes (PRO) | X | EQ-5D only | Both the Lung Cancer Symptom Scale and EQ-5D will be given in Follow-up Visits 1 & 2. In Survival Visits, EQ-5D is collected every 3 months for the first year of the Follow-up Phase, then every 6 months thereafter. |
| Subject Status | | | |
| Survival Status | X | X | Every 3 months after X02; may be accomplished by visit or phone contact, to update survival information and assess subsequent anti-cancer therapy. |

ALP = alkaline phosphatase, ALT = alanine aminotransferase, AST = aspartate aminotransferase, BP = blood pressure, BUN = blood urea nitrogen, Ca = calcium, Cl = chloride, CT = computed tomography, ECG = electrocardiogram, IVRS = interactive voice response system, K = potassium, LDH = lactate dehydrogenase, Mg = magnesium, MRI = magnetic resonance imaging, Na = sodium, NCI CTCAE = National Cancer Institute Common Toxicity Criteria for Adverse Events, O2 = oxygen, P = phosphorus, SAE = serious adverse event, T.Bili = total bilirubin, TSH = thyroid stimulating hormone, T3 = triiodothyronine, T4 = thyroxine, WOCBP = women of childbearing potential

^a Follow-up visits occur as follows: X01 = 35 days (\pm 7 days) from last dose, X02 = 80 days (\pm 7 days) from X01

^b S, Survival visits continue every 3 months (\pm 7 days) after Follow-up Visit 2 until death, lost to follow-up, or withdrawal of study consent

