Time to Symptom deterioration (TTSD) is defined as the time between the date of randomization and the first date of a 10 point or more increase from baseline in the LCSS Average Symptom Burden Index (ASBI). Subjects who did not meet the criteria of a 10 points or more increase from baseline in LCSS ASBI will be censored on their last LCSS assessment date. Subjects who did not have any on study LCSS assessment will be censored on their date of randomization.

The **LCSS** is a measure of disease-related symptoms and quality of life suited to use in patients suffering from lung cancer. It includes six items measuring loss of appetite, fatigue, coughing, shortness of breath, hemoptysis, and pain. Three additional items measure overall symptom burden, disease-related functional limitations, and quality of life. The questionnaire uses a 24 hour recall period, and responses for each item are captured using a 100-mm visual analog scale (VAS). Scores for individual items ranging from 0 (no symptomatology or highest quality of life) to 100 (worst symptomatology or quality of life) are derived by dividing the length of the line drawn from the lowest possible response to the patient's response by the length of the VAS and multiplying the resulting quotient by 100.

An average symptom burden index (ASBI) score can be derived as the average of scores for the six symptom-related items with a clinically meaningful change in ASBI score being defined as 10 points.

Disease-related symptom deterioration rate by Week 12 and by Week 24 is defined as the proportion of randomized subjects who had 10 points or more increase from baseline in ABSI score at any time between randomization and Week 12/Week 24, respectively.

Subjects' overall health status will be assessed using The EuroQol Group's self-reported health status measure (**EQ-5D**). EQ-5D essentially has 2 health status components - the EQ-5D descriptive system and the EQ visual analogue scale (EQ VAS). The EQ-5D descriptive system comprises the following 5 dimensions: mobility, self-care, usual activities, pain/discomfort and anxiety/depression. Each dimension has 3 levels: no problems, some problems, severe problems. The EQ VAS records the subject's self-rated health state on a 100-point vertical, visual analogue scale (0 = worst imaginable health state; 100 = best imaginable health state).²⁹

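### TTSD and the Week 12/24 symptom-deterioration rates count any single 10-point ASBI rise, but LCSS is 2-weekly on nivolumab and 3-weekly on chemotherapy for the first 6 months on treatment; add a sensitivity analysis on a common 6-week grid

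*Protocol*

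**What the plan says.** **Event rule.** Protocol 8.3.3 defines TTSD as the time from randomization to the first ASBI rise of at least 10 points. It defines the Week 12 and Week 24 deterioration rates as the proportion of randomized subjects with a "10 points or more increase from baseline in ABSI score at any time between randomization and Week 12/Week 24" (ABSI there is evidently ASBI). Neither definition asks for a second, confirming score.

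**Assessment schedule.** The PRO rows of Protocol Tables 5.1-2 and 5.1-3 carry the same rule for both arms: "Assessments will be performed at each cycle on Day 1 for the first 6 months on study, then every 6 weeks thereafter". The cycles differ. The nivolumab column is headed "Each Cycle (Every 2 Weeks) on Day 1"; the chemotherapy column is headed "Cycle 2 to x Day 1 of a 21-day Cycle (Every 3 Weeks" and so on. After treatment stops, Table 5.1-4 applies to both arms: "Both the Lung Cancer Symptom Scale and EQ-5D will be given in Follow-up Visits 1 & 2". Footnote a of that table times the visits from the last dose: "Follow-up visits occur as follows: X01 = 35 days", with Visit 2 a further 80 days later (each ±7 days).

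**Purpose and analysis.** Protocol 1.3.3 states both measures as comparisons between nivolumab and chemotherapy. Visible SAP 7.9.1 plans Kaplan-Meier curves, medians and Week 6, 12 and 24 rates with confidence intervals for what it calls TTD. It shows no test, hazard ratio, visit window, common grid or confirmation rule.

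**The concern.** A rule of the form first rise, or any rise, can only gain events as looks are added, because each look is another chance for a noisy score to cross the threshold. Here the number of looks depends on the arm, and both horizons lie inside the 6-month period in which the schedules differ. Two arms with the same symptom courses and the same time on treatment would therefore be expected to show different deterioration rates, with nivolumab the worse. What is at stake is the reading of an exploratory between-arm symptom comparison, not a formal test.

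**Working it through.** The plan gives no power, event or rate figure for these endpoints, so there is nothing of its own to reproduce.

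**1. Scheduled looks.** Inputs from the protocol: cycle length *c* = 14 or 21 days; horizon *h* = 84 or 168 days from randomization; gap *g* from randomization to first dose (Sections 3.1.1.2 and 4.4.2 allow 3 business days). Nominal post-baseline on-treatment looks = floor((*h* − *g*)/*c*).
- *g* = 0: 84/14 = 6 versus 84/21 = 4; 168/14 = 12 versus 168/21 = 8.
- *g* = 1: floor(83/14) = 5 versus floor(83/21) = 3; floor(167/14) = 11 versus floor(167/21) = 7. A gap of up to 5 calendar days gives the same counts.

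**2. Simplest illustration.** Assume no true change, everyone on treatment and independent error with SD σ on each score (σ is an assumption). For *k* looks, P(at least one rise ≥ 10) = 1 − E[Φ((10 + e₀)/σ)^k], with e₀ ~ N(0, σ²) the baseline error.

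| Assumed σ | Week 12, 6 vs 4 looks | Week 24, 12 vs 8 looks |
|---|---|---|
| 4 | 15.0% vs 11.5% (+3.5) | 22.3% vs 17.8% (+4.5) |
| 6 | 36.5% vs 29.9% (+6.6) | 48.4% vs 41.4% (+7.0) |
| 8 | 50.2% vs 42.5% (+7.7) | 62.7% vs 55.6% (+7.1) |

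**3. Correlation, discontinuation and follow-up visits.** Simulation with the same symptom errors in both arms. All inputs are assumed: SD of change at Week 12 of 8 to 15; weekly autocorrelation 0 to 0.9; 0 or 20% of cycles delayed 7 days; time on treatment either unlimited or exponential with median 6 to 18 weeks, equal in both arms. Follow-up Visits 1 and 2 are placed from the last dose: cycle Day 1 for nivolumab, Day 5 for topotecan (given "on Days 1 through 5 every 3 weeks (21 days") and Day 3 for amrubicin ("on Days 1 through 3 every 3 weeks (21 days"). Excess for nivolumab, in percentage points:
- No true change, all stay on treatment: +1.7 to +8.4 by Week 12; +2.6 to +7.1 by Week 24.
- No true change, with discontinuation: +0.5 to +7.6; +0.4 to +6.1.
- Middle case (SD 12, autocorrelation 0.7): +3.2 to +4.9 by Week 12 with discontinuation, about +5.5 with none; +2.6 to about +5.3 by Week 24. With a 9-week median on treatment, mean looks by Week 12 are 4.1 versus 2.8 and the proportions 36.5% versus 32.6%.
- Middle case with a true mean worsening of 5 or 10 points by Week 12 in both arms: +3.6 to +5.4; +0.9 to +3.8.
- Sustained, noise-free worsening: 0 to +1.3; −0.2 to +0.9.

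**4. Scale.** With 280 per arm, the standard error of the difference is √[(0.365 × 0.635 + 0.326 × 0.674)/280] = 0.040, or 4.0 points. The middle case is therefore about 1 SE or slightly more.

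**5. Does a common grid help?** Up to Week 24 the 14- and 21-day schedules coincide only on Days 42, 84, 126 and 168, that is Weeks 6, 12, 18 and 24. One assessment per nominal week gives 2 versus 2 looks by Week 12 and 4 versus 4 by Week 24. With 20 days either side, the Kaplan-Meier excess falls to between −0.5 and +1.2 in the middle case and between −1.5 and +1.9 over all 408 scenarios run. In 4 of the 408 the grid was further from zero at Week 12 than the planned analysis (all at autocorrelation 0.9; +0.5 to +1.2 became −0.8 to −1.5).

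A 14-day half-width is too narrow. If the last chemotherapy cycle starts on Day 21, the last dose is on Day 25 (topotecan) or Day 23 (amrubicin), so Follow-up Visit 1 falls on Day 60 or 58, outside Days 28 to 56. At Week 12 that narrower grid was further from zero than the planned analysis in 84 of the 408 scenarios.

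**The case against.** **The SAP may already deal with this.** The visible SAP passes from Section 4.2.4 straight to Section 5, with no exploratory-endpoint section, and uses TTD in 7.9.1 without a visible definition. Parts of it, including text after the secondary objectives in Section 3.2, are redacted. Windows or a confirmation rule could sit there. A reader might infer that the plan has no LCSS windows; the documents support that for visible text only. This stands as a limit on the point.

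**The consequence is small.** The endpoints are exploratory, visible SAP 7.9.1 contains no test, and it reports Kaplan-Meier rates rather than the protocol's crude proportions. This also stands. A reader might go further and infer that the trial's efficacy conclusions are compromised. They are not: OS, PFS, ORR and the hierarchy do not use LCSS.

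**Half as many looks again does not mean half as many events again.** Looks within a subject share one baseline score and are correlated. In the table, 36.5/29.9 = 1.22; in the middle case with a 9-week median, 36.5/32.6 = 1.12. Every variability and treatment-duration input is assumed, so direction is firmer than size.

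**The counts are conditional.** 6 versus 4 and 12 versus 8 need dosing on the day of randomization. Any gap, with nominal visits, gives 5 versus 3 and 11 versus 7. The direction does not change.

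**The grid has its own asymmetry.** Days 21, 63, 105 and 147 fall outside every window and are nominal chemotherapy visits; no nominal nivolumab visit from Day 28 on is lost. In a harsh check (middle-case variability, 6-week median, exactly nominal treatment visits, half of follow-up visits completed, 8-month median survival), 25.5% of chemotherapy and 18.8% of nivolumab subjects had no usable grid assessment, and the Week 12 excess was +2.4 crude and +1.5 by Kaplan-Meier. With a 0-to-5-day dosing gap and ±3-day visits the Kaplan-Meier residual was about +0.2. The grid mostly works, but not perfectly.

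**A footnote might be enough.** For a descriptive output, stating assessment frequency by arm is a defensible minimum. It would not show the reader how much of an observed difference depends on that frequency.

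**Conclusion.** The point holds as a low-severity improvement. The written event rule, applied to the written schedule, ascertains deterioration more often on nivolumab than on chemotherapy during the first 6 months on treatment. With equal symptom courses and equal time on treatment, that tends to make nivolumab look worse: about 3 to 6 points by Week 12 in a middle case, and near zero if worsening is sustained and noise-free. The look counts and the direction follow from the protocol; the percentages rest on assumed SDs, autocorrelations and times on treatment. Follow-up Visits 1 and 2 dilute the imbalance without removing it. The absence of a remedy can be stated for the visible SAP text only.

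**What to change.** Unless redacted SAP text already sets LCSS windows, add to SAP 7.9.1, beside the planned analysis:

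> As a sensitivity analysis, TTSD and the Week 6, 12 and 24 Kaplan-Meier estimates will be derived on nominal Weeks 6, 12, 18 and 24 from randomization, then 6-weekly. In both arms, only the one LCSS assessment (on-treatment or Follow-up Visit 1 or 2) closest to each nominal week and within 20 days either side will be used, the earlier if tied. Event time is the nominal week.

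The windows are 41 days wide and do not overlap: Days 22–62, 64–104, 106–146 and 148–188, with Week 6 as Day 42. Report with it a note that assessment frequency differs by arm, and the number of subjects in each arm without a usable grid assessment.

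The cost is SAP wording and programming on data already collected; no visit changes. The downsides should be stated:
- Fewer assessments are used, event times are coarser, and transient worsening between grid points is missed.
- The Week 12 window reaches Day 104, and assessments on Days 21, 63, 105 and 147 are not used.
- A residual of roughly 1 to 2 points either way can remain.
- Unequal time on treatment is not corrected. It is possible because Protocol 4.5.4 allows only nivolumab to continue beyond progression. In the middle case with assumed medians of 18 versus 9 weeks, the Week 12 excess falls from +7.5 to +2.1, not to zero.

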8.4 Analyses

8.4.1 Demographics and Baseline Characteristics

Demographics and baseline laboratory results will be summarized by treatment arm as randomized using descriptive statistics for all randomized subjects.

8.4.2 Efficacy Analyses

All hypothesis testing will be two-sided based on a significance level of 0.05 except for OS. If superiority of OS is demonstrated, a hierarchical hypothesis testing approach for the key secondary endpoints will be used to preserve a study-wise type I error rate at 0.05. The key secondary endpoints will be tested in the following hierarchical order:

- 1) PFS
- 2) ORR.

The formal statistical testing for PFS will take place only if OS is statistically significant and the statistical testing for ORR will take place only if both OS and PFS are statistically significant.

8.4.2.1 Methods of Primary Endpoint

The distribution of OS will be compared in two randomized arms via a two-sided, log-rank test stratified by the stratification factors as described in Section 3.1. The HR and the corresponding two-sided 95% CI will be estimated in a stratified Cox proportional hazards model using randomized arm as a single covariate. The OS curves for each randomized arm will be estimated using the Kaplan-Meier (KM) product-limit method. Two-sided, 95% confidence intervals for median OS will be computed by Brookmeyer and Crowley method (using a log-log transformation). Survival rates at 6, 12, 18, 24, 36, 48 months and 5 years will be estimated using KM estimates on the OS curve for each randomized arm provided minimum follow-up is longer than timepoint to generate the rate. Associated two-sided 95% CIs will be calculated using the Greenwood formula.

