The primary endpoint of the study is OS.

The study design schematic is presented in [Figure 3.1-1](#).

Accrual duration is expected to be approximately 18 months; overall study duration will be approximately 34 months (18 months accrual + minimum follow up of 16 months). The study will end when analysis of survival is complete. Additional survival follow-up may continue for up to 5 years from the time of this analysis.

A DMC will be utilized to provide general oversight and safety considerations for this study, CA209331 (Section 7).

Figure 3.1-1: Study Schematic

^a Subjects must have had at least 4 cycles of platinum-based, first-line chemotherapy, or if they received less than 4 cycles of platinum-based first-line chemotherapy, they must have had a best overall response (BOR) of at least a partial or complete response after completion of chemotherapy.

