8 STATISTICAL CONSIDERATIONS

8.1 Sample Size Determination

In this study, the primary endpoint of OS will be evaluated for treatment effect at the overall alpha level of 0.05 (two-sided). Approximately 560 subjects will be randomized at a ratio of 1:1 into two arms: Arm A (nivolumab); Arm B (chemotherapy: topotecan or amrubicin). For sample size calculation, non-proportional hazard model with a piecewise exponential distributions in both arms are assumed. Based on published survival curves for topotecan, a 2-piece exponential distribution with an 8-month median OS and taking into account that a limited number of subjects might receive immuno-oncology as subsequent therapy, a conservative 5% 2-year survival rate is assumed for the control arm. A delayed effect for nivolumab with a hazard ratio (HR) of 1 for the first 8 months and an HR of 0.5 thereafter is assumed. The final analysis will take place 34 months after the first patient have been randomized and no formal interim analysis will be conducted. The 560 subjects are expected to be randomized in 18 months, resulting in about 16 months of follow-up for the last subject randomized at the time of the primary analysis. It is anticipated that approximately 480 events will be observed at the time of the analysis, leading to 90% power to detect a difference in overall survival as tested via a log-rank test with a two-sided 0.05 type I error rate. Power calculations were performed using EAST® Software (version 6.4.1).

The decision to incorporate the China subset into the overall population for analysis is the result of a review of the protocol statistical assumptions in comparison to recent data from the CA209032 study in 2L+ SCLC subjects.²⁸ The data from CA209032, which were not available at the time of protocol design, suggest a delayed effect of nivolumab with a non-proportional hazard for survival. Additionally, review of recently generated real-world data for topotecan resulted in updated assumptions for the control arm. Given the updated statistical assumptions, incorporation of the China subset into the study analyses grants adequate statistical power by increasing the study sample size.

| Table 8.1-1: Sample Size Justification | |
|---|---------------------------------------|
| Primary Endpoint | OS |
| Power | 90% |
| Alpha level | 0.05 |
| Sample size | 560 |
| Accrual duration | 18 months |
| Timing of the analysis from randomization of first subject (months) | 34 |

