| Hypothesized OS rate at 8 months | 50% in both arms (HR=1 up to Month 8) |
| Hypothesized OS rate at 24 months | 5% vs 16% (HR=0.5 from Month 8) |
| Expected Average HR | ~0.745 |
| Expected number of event at 34 months | 482 |

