7.5 Efficacy

7.5.1 Overall Survival

7.5.1.1 Primary Analysis

The distribution of OS will be compared in two randomized arms at the interim and final analyses via a two-sided, log-rank test stratified by baseline stratification factors, as entered into the IVRS.

The hazard ratio (HR) and the corresponding 100(1- α)% CI (adjusted for the interim) will be estimated in a stratified Cox proportional hazards model using randomized arm as a single covariate.

The OS curves for each treatment group will be estimated using the Kaplan-Meier (KM) product-limit method. Two-sided, 95% confidence intervals for median OS will be constructed based on a log-log transformed CI for the survivor function S(t)¹⁰.

Based on the availability of the data, survival rates at 6, 12, 18, 24, 36, 48 months and at 5 year will also be estimated using KM estimates on the OS curve for each randomized arm. Minimum follow-up must be longer than timepoint to generate the rate. Associated two-sided 95% CIs will be calculated using the Greenwood's formula¹¹ for variance derivation and on log-log transformation applied on the survivor function S(t)

The status of subjects who are censored in the OS Kaplan-Meier analysis will be tabulated for each treatment group using following categories:

- on-study (on-treatment and not progressed, on-treatment progressed, in follow-up);
- off-study: (lost to follow-up, withdraw consent, etc.).

Unless otherwise specified, the primary population will be the all randomized population.

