7.5.1.2 OS Sensitivity Analyses

Non-Proportional Hazard Assumption

To examine the assumption of proportional hazards in the Cox regression model, in addition to treatment, a time-dependent variable defined by treatment by time interaction will be added into the model. A two-sided Wald Chi-square p-value of less than 0.1 may indicate a potential nonconstant treatment effect. In that case, [REDACTED].

In case non-proportionality cannot be ruled out by the test described above, piecewise hazard ratios (e.g. from 0 to 8 months and after 8months) will be presented together with their corresponding 95% CI.

To investigate the impact of potential non-proportional hazard, the distribution of OS will also be compared using a two-sided weighted log-rank test stratified by the stratification factors, as entered into the IVRS. The weighted log-rank test will use G ($\rho = 0$, $\gamma = 1$) weights, in the terminology of Fleming and Harrington^{14,15}. This p-value will be considered as descriptive.

Additional Sensitivity Analyses

The following OS sensitivity analyses will be performed.

- OS will be compared between treatment groups using a two-sided α (adjusted for the interim) unstratified log-rank test.
- OS will be compared between treatment groups using the strata as determined at baseline (CRF source). This analysis will be performed only if at least one stratification variable at IVRS and at baseline disagrees for at least 10% of the randomized subjects.
- OS will be compared between treatment groups using a two-sided α (adjusted for the interim) stratified log-rank test in the All Treated Subjects population, using arm as randomized. This analysis will be performed only if the proportion of randomized but never treated subjects exceeds 10%.

Estimate of the hazard ratio, its two sided $100(1-\alpha)\%$ CI (adjusted for the interim) and p-value will be presented.

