7.5.1.5 Subject Follow-up for OS

The minimum follow-up will be reported. The minimum follow-up is defined as the time interval between the last patient's randomization date and the clinical cutoff date.

The extent of follow-up defined as the time between randomization date and last known date alive (for subjects who are alive) or death date (for subjects who died) will be summarized descriptively (median, min, max) for all subjects randomized.

The currentness of follow-up, defined as the time between last OS contact (i.e., last known date alive or death date) and data cut-off date, will be summarized by treatment group. Subjects who died before data cut-off date will automatically have zero value for currentness of follow-up. For subjects with last known date alive after data cut-off date, they will have zero value for currentness of follow-up as well. The currentness of follow-up will be categorized into the following categories: 0 days, 1-3 months, 3-6 months, 6-9 months, 9-12 months and ≥ 12 months.

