7.5.2 Progression Free Survival

7.5.2.1 Primary Analysis of PFS

PFS for each treatment arm will be estimated using Kaplan-Meier product limit method and graphically displayed. A two-sided 95% CI for median duration will be constructed based on a log-log transformed CI for the survivor function $S(t)$ ^{9,10}.

The comparison of PFS distribution will be performed via a stratified log-rank test at two-sided, 5% level. In addition, the stratified hazard ratios between treatment groups will be provided along with the 95% CI.

PFS rates at 6, 12, 18, 24, 36, 48 months and at 5 year will also be estimated using KM estimates on the PFS curve for each randomized arm. Minimum follow-up must be longer than or equal to timepoint to generate the rate. Associated two-sided 95% CIs will be calculated using the Greenwood's formula¹¹.

The source of progression (death vs. progression) will be summarized by treatment group.

The status of subjects who are censored in the PFS Kaplan-Meier analysis will be tabulated for each treatment group using following categories:

- Never treated
- On-study (on treatment, in follow-up)
- Off-study: (lost to follow-up, withdrew consent, other).
- Received subsequent anti-cancer therapy
- No baseline tumor assessment

To assess consistency of treatment effect on PFS in different subsets, a “forest” plot of the PFS unstratified hazard ratio (and 95% CI) will be produced for the same variable as in the OS analysis.

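### Does the minimum-follow-up condition wrongly withhold the 18- and 24-month survival rates at the final analysis?

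*Protocol*

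**What the plan says.** Protocol 8.4.2.1 plans Kaplan-Meier OS rates at 6, 12, 18, 24, 36 and 48 months and 5 years, "provided minimum follow-up is longer than timepoint to generate the rate". SAP 7.5.1.1 gives the same list, subject to data being available, and the same condition: "Minimum follow-up must be longer than timepoint to generate the rate". SAP 7.5.1.5 supplies the definition, "The minimum follow-up is defined as the time interval between the last" randomization and the clinical cutoff.

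Protocol 8.1 puts the final analysis 34 months after the first randomization, with 18 months of accrual, "resulting in about 16 months of follow-up for the last subject randomized at the time of the primary analysis". Table 8.1-1 has a row "Hypothesized OS rate at 24 months", with 5% for chemotherapy and 16% for nivolumab. Protocol 3.1 adds: "Additional survival follow-up may continue for up to 5 years from the time of this analysis". Under Protocol 3.1.1.3 and Table 5.1-4, survival contacts continue every 3 months until death, loss to follow-up or withdrawal of consent.

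Other outputs describe late survival. Both documents plan the full Kaplan-Meier curves. SAP 7.5.1.2 adds a Fleming-Harrington (0, 1) log-rank test and, if non-proportionality cannot be ruled out, "piecewise hazard ratios (e.g. from 0 to 8 months and after 8months) will be presented". For PFS, SAP 7.5.2.1 words the condition slightly differently: "Minimum follow-up must be longer than or equal to timepoint to generate the rate".

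**The concern.** The condition is tied to the entry date of the last subject, and Kaplan-Meier estimation does not need every subject to have reached a timepoint. Applied at month 34, it removes the 18- and 24-month rates from the only analysis to which the plan commits. The trial assumes a hazard ratio of 1 up to month 8 and 0.5 after it, so a reader would look for the benefit late, and month 24 is where the design states it in absolute terms. The late-weighted test gives a p-value and the piecewise hazard ratios give relative effects. Neither gives an absolute survival rate with a confidence interval at those times. If this were a defect, the cost would be an incomplete absolute description of the primary endpoint. The primary test would not change.

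**Working it through.** **1. Minimum follow-up.** Cutoff minus accrual duration is 34 - 18 = 16 months, which is the plan's own figure.

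**2. Effect of the condition.** 6 and 12 are below 16, so those rates are produced. 18, 24, 36, 48 and 60 are above 16, so those are not. With 18-month accrual, the 18-month rate becomes available at any cutoff after month 18 + 18 = 36, and the 24-month rate after month 18 + 24 = 42. Both lie within the follow-up of up to 5 years that Protocol 3.1 allows after the analysis.

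**3. Design model.** Table 8.1-1 implies these monthly hazards:
- both arms to month 8: ln 2 / 8 = 0.0866
- control after month 8: ln(0.50/0.05)/16 = 0.1439
- nivolumab after month 8: half of that, 0.0720

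Check at 24 months: 0.5 × exp(-16 × 0.1439) = 5.0% and 0.5 × exp(-16 × 0.0720) = 15.8%, matching the stated 5% vs 16%.

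**4. What the rows would contain.** The calculation takes 280 per arm and assumes uniform accrual and no dropout, neither of which the documents state. From month 16 the number at risk is 280 × S(t) × (34 - t)/18. Standard errors use Greenwood's formula.

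| Month | Nivolumab vs control | Difference (SE), points | At risk | Tabulated at month 34 |
|---|---|---|---|---|
| 12 | 37.5% vs 28.1% | 9.4 (3.9) | 105 vs 79 | yes |
| 18 | 24.3% vs 11.9% | 12.5 (3.2) | 61 vs 30 | no |
| 24 | 15.8% vs 5.0% | 10.8 (2.8) | 25 vs 8 | no |

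These assumptions give 500 events against the planned 482, so two alternatives were run:
- Dropout of 5.3% per year (482 events): 56 vs 27 at risk at month 18, and 22 vs 7 at month 24.
- Linearly rising accrual without dropout (485 events): 54 vs 26 and 14 vs 4.

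The 18-month rate is well supported throughout. The 24-month control rate is not: in the base case its 95% interval, on the log-log scale, is about 2.6% to 8.5%.

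**5. What is already reported.** Month 12 falls after the assumed onset of effect, and its 9.4-point difference is close to the 10.8 points at month 24. The late absolute benefit is therefore partly shown, with confidence intervals for each arm.

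**6. Whether the condition has a reason.** Beyond month 16 the estimate leans on earlier entrants, so it is unbiased only if entry time is unrelated to prognosis. Suppose the last third of entrants had a hazard ratio of 0.5 relative to the control hazards (an assumption). True 24-month survival would be 2/3 × 5.0% + 1/3 × √0.05 = 3.3% + 7.5% = 10.8%. Those entrants have only 16 to 22 months of potential follow-up, and the Kaplan-Meier estimate converges to 8.9%. At month 18 the bias is only about 0.1 point.

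The primary log-rank test does not need this assumption to be valid. Randomization makes entry time independent of arm, so the arms remain exchangeable under the null. Simulated type I error with the last third of entrants at hazard ratios of 0.5, 0.67, 1.5 and 2 stayed between 4.8% and 5.6%. Drift is conceivable here, because the Protocol Synopsis lets China enrollment continue until its number is filled.

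**7. The obvious alternative.** A number-at-risk threshold, say 5 per arm, would depend on outcomes. At month 24 the control arm has 7.8 at risk in the base case, 7.0 with dropout and 4.3 with rising accrual. If true control survival were 3%, it would have 280 × 0.03 × 10/18 = 4.7. Such a threshold would not reliably release the 24-month rate either.

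**The case for a change.** The best case against the plan is month 18. The difference is largest there, and at least 54 vs 26 subjects remain at risk under every accrual and dropout pattern examined. Staggered entry costs almost no precision: the standard error is 3.23 points against 3.21 with complete follow-up. Entry-time drift hardly matters at that point. Later follow-up is permitted but no later cutoff is promised, so the condition could keep a sound estimate out of the only committed table. All of this stands, and an 18-month row would be a reasonable descriptive addition.

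It does not show a mistake. No objective in Protocol 1.3 asks for a rate at 18 or 24 months, and the 24-month figures in Table 8.1-1 are sizing assumptions. The curves through those months will be shown. A calendar condition fixed without reference to outcomes is a defensible safeguard against sparse or drift-prone tail estimates, and at month 24 it does real work.

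The PFS wording adds nothing. No listed timepoint equals 16 months, so the two phrasings give the same result at the planned cutoff. Protocol 8.4.2.2 lists no PFS landmark rates, and the documents give no PFS assumptions from which a loss could be calculated.

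**Conclusion.** The concern does not hold. The arithmetic behind it is right: at the planned month-34 cutoff only the 6- and 12-month OS rates are tabulated. But that is the condition working as written, consistently for OS in both documents, on a list meant to be filled in as follow-up matures. Type I error, power, the hazard ratio and the survival curves are unaffected.

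Dropping the condition would reliably gain one descriptive row at 18 months. A 24-month row would have about 4 to 8 control subjects at risk and would be exposed to bias if late entrants differed. Whether to add such rows is a trade-off on which statisticians can differ.

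The at-risk numbers rest on the design hazards, 280 per arm and assumed accrual and dropout patterns. The conclusion on which rates are tabulated needs only the planned 16 months, and it is the same for any accrual duration from 16 to just under 22 months with the cutoff at month 34.
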